### **7.5.1.2 Supportive Analyses of Disease-Free Survival**

The following sensitivity analyses will be conducted using the primary and secondary definition of DFS:

- 1) DFS using stratification factors as obtained from the baseline CRF pages (instead of IRT). The hazard ratio associated with treatment will be presented along with the associated two-sided 95% CIs. This analysis will be performed only if at least one stratification variable/factor at randomization (as per IRT) and baseline are not concordant for at least 10% of the randomized subjects.
- 2) DFS using an unstratified log rank test. The hazard ratio associated with treatment will be presented along with the associated two-sided 95% CIs.
- 3) A multivariate Cox regression model will be used in order to estimate the treatment effect after adjustment for possible imbalances in known or potential prognostic factors. The factors used in the randomization, which, by definition, will be balanced across treatment groups, will still be included in the model as stratification factors. However, all additional factors will be incorporated as covariates. The additional factors, which are all measured at baseline, will include:
  - Age (< 65 vs. ≥ 65 year)
  - Gender (Male vs. Female)
  - Baseline ECOG status (0 vs. 1 vs. 2)
  - Pathological status (pT0-2 vs. pT3 vs. pT4)

The level of the covariate normally associated with the worst prognosis will be coded as the reference level. The hazard ratio associated with treatment and with each of the baseline covariates will be presented along with associated 95% CIs.

- 4) DFS for subjects with no relevant protocol deviations. This analysis will be conducted only if there are more than 10% subjects with relevant protocol deviations. The hazard ratio associated with treatment will be presented along with the associated two-sided 95% CIs.
- 5) DFS accounting for missing disease assessments prior to DFS event (recurrence or death). This analysis will be performed only if at least 10% of DFS events (in the population of interest) have two or more missing prior disease assessment (no protocol specified disease assessment imaging completed at the expected timepoint). It will apply the following restriction to the primary definition in case a subject has two or more missing disease assessments, the subject will be censored at the last disease assessment date prior to DFS event.
- 6) Delayed effect of immunotherapy interventions may cause a late separation in the DFS KM curves and non-proportional hazards. DFS will be compared between treatment groups via two-sided 0.05 stratified weighted log-rank test among subjects. The two-sided stratified weighted log-rank p-value will be reported using G (rho = 0, gamma = 1) weights, in the terminology of Fleming and Harrington.

The Fleming Harrington test can be unstable, so it is possible, though uncommon, that the p-value for this trial will not be estimable.

The estimate of the DFS hazard ratio in the period before and following 6 months will be calculated using a stratified time-dependent Cox model with effects for treatment and period-by-treatment interaction. In this model, period is a binary variable indicating pre- vs. post-6 months. Ties will be handled using the exact method. A two-sided 95% CI for the hazard ratio will also be presented.

- 7) To examine the assumption of proportional hazards in the Cox regression model, in addition to treatment, a time-dependent variable defined by treatment by time interaction will be added into the model. A two-sided Wald Chi-square p-value of less than 0.1 may indicate a potential non-constant treatment effect. In that case, additional exploratory analyses may be performed.

### **7.5.1.3 Subset Analyses of Disease-Free Survival**

The influence of baseline and demographic characteristics on the treatment effect will be explored via exploratory subset analyses. The median DFS based on KM product-limit method along with two-sided 95% CIs will be produced for the following subgroups:

- PD-L1 Status (Positive  $\geq 1\%$  vs. Negative  $< 1\%$  vs. Indeterminate / Not Evaluable; source: clinical database)
- Use of prior neo-adjuvant cisplatin therapy (Yes vs. No; source: CRF)
- Prior Cisplatin status (received Neo-Adjuvant, Unwilling vs. Ineligible vs. Other; source: CRF)
- Use of any prior neo-adjuvant systemic therapy (Yes and No) (source: CRF)
- Pathological lymph node status (N+ vs. N0/x with  $< 10$  Nodes Removed vs. N0 with  $\geq 10$  Nodes Removed; source: CRF)
- Pathological status (pT0-2 vs. pT3 vs. pT4; source:CRF)
- Age ( $< 65$ ,  $\geq 65$  and  $< 75$ ,  $\geq 75$  years)
- Region (US, EU, ROW).

- Gender (Male, Female)
- Race (White, Black or African American, Asian, American Indian or Alaska Native, Native Hawaiian or Other Pacific Islander, Other)
- Baseline ECOG status (0, 1, 2)
- Smoking Status (Never, Former/Current, Unknown)
- Baseline Hemoglobin (< LLN vs. ≥ LLN)
- Baseline Creatinine Clearance (≥ 60 vs. < 60ml/min)
- Time from IUC surgery to randomization (0 - 30, > 30 - 60, > 60 - 90, > 90 - 120, > 120 days)
- Initial tumor origin (Urinary Bladder vs. Renal Pelvis, Ureter)
- Minor histological variants (Presence vs. Absence)

A forest plot of the DFS hazard ratios (along with the 95% CIs) will be produced for each level of the subgroups listed above. The analysis comparing treatment (i.e., Hazard Ratio) will be conducted if the number of subjects in the subgroup category is more than 10.

#### **7.5.1.4 Current Status of DFS Follow-up**

The currentness of follow-up for DFS, defined as the time between last evaluable disease assessment (i.e., regardless of initiation of subsequent therapy or new non-urothelial carcinoma primary cancer) and cutoff date (defined by last patient last visit date), will be summarized by treatment group in months. Subjects who had DFS events and subjects with last evaluable disease assessment date on or after data cut-off date will have zero value for currentness of follow-up.

A by-subject listing will also be produced to accompany the subject time from last evaluable disease assessment.

#### **7.5.2 Overall Survival**

The key secondary objective of the study is to compare the overall survival between treatment groups in each co-primary populations (all randomized subjects and all randomized subjects with PD-L1 expression ≥ 1%).

##### **7.5.2.1 Analysis of Overall Survival**

Overall survival will be compared between the treatment groups at the interims and final analyses, using stratified log-rank test, as defined in [Section 5](#). The stratification factors will be those used in the analysis of DFS.

An O'Brien and Fleming  $\alpha$ -spending function will be employed to determine the nominal significance levels for the interim and final analyses. The estimate of the OS hazard ratio between treatment groups will be calculated using a stratified Cox proportional hazards model, with treatment as the sole covariate. Ties will be handled using the exact method. A two-sided (1-adjusted  $\alpha$ )% CI (adjusted for interims) for the hazard ratio will also be presented.

The OS function for each treatment group will be estimated using the KM product limit method and will be displayed graphically. A two-sided 95% CI for median OS in each treatment group

will be computed via the log-log transformation method. OS rates at fixed time points (e.g. 6 months, depending on the minimum follow-up) will be presented along with their associated 95% CIs. These estimates will be derived from the Kaplan Meier estimate and corresponding CIs will be derived based on Greenwood formula for variance derivation and on log-log transformation applied on the survivor function.

The status of subjects who are censored in the OS KM analysis will be tabulated for each treatment group using the following categories:

- On-study (on-treatment, in follow-up)
- Off-study (lost to follow-up, withdraw consent, never treated)

A by-subject listing will be presented including treatment group, first and last dose date, whether the subject died, and if censored, the reason, event/censored date and OS duration.

### **7.5.2.2 Supportive Analyses of Overall Survival**

The following sensitivity analyses will be conducted using the primary definition of OS:

- 1) OS using stratification factors as obtained from the baseline CRF pages (instead of IRT). The hazard ratio associated with treatment will be presented along with the associated two-sided 95% CIs. This analysis will be performed only if at least one stratification variable/factor at randomization (as per IRT) and baseline are not concordant for at least 10% of the randomized subjects.
- 2) OS using an unstratified log rank test. The hazard ratio associated with treatment will be presented along with the associated two-sided 95% CIs.
- 3) A multivariate Cox regression model will be used in order to estimate the treatment effect after adjustment for possible imbalances in known or potential prognostic factors. The factors used in the randomization, which, by definition, will be balanced across treatment groups, will still be included in the model as stratification factors. However, all additional factors will be incorporated as covariates. The additional factors, which are all measured at baseline, will include:
  - Age (< 65 vs. ≥ 65 year)
  - Gender (Male vs. Female)
  - Baseline ECOG status (0 vs. 1 vs. 2)
  - Pathological status (pT0-2 vs. pT3 vs. pT4)

The level of the covariate normally associated with the worst prognosis will be coded as the reference level. The hazard ratio associated with treatment and with each of the baseline covariates will be presented along with associated 95% CIs.

- 4) OS for subjects with no relevant protocol deviations. This analysis will be conducted only if there are more than 10% subjects with relevant protocol deviations. The hazard ratio associated with treatment will be presented along with the associated two-sided 95% CIs.

- 5) To examine the assumption of proportional hazards in the Cox regression model, in addition to treatment, a time-dependent variable defined by treatment by time interaction will be added into the model. A two-sided Wald Chi-square p-value of less than 0.1 may indicate a potential non-constant treatment effect. In that case, additional exploratory analyses may be performed.

### **7.5.2.3 Subset Analyses of Overall Survival**

The influence of baseline and demographic characteristics on the treatment effect will be explored via exploratory subset analyses. The median OS based on KM product-limit method along with two-sided 95% CIs will be produced for the same subgroups used for DFS (see [Section 7.5.1.2](#)).

A forest plot of the OS hazard ratios (along with the 95% CIs) will be produced for each level of the subgroups listed above. The analysis comparing treatment (i.e., Hazard Ratio) will be conducted if the number of subjects in the subgroup category is more than 10.

### **7.5.2.4 Current Status of OS Follow-up**

The extent of follow-up for survival, defined as the time between randomization date and last known alive date (for subjects who are alive) or death date (for subjects who died), will be summarized descriptively (median, min, max, etc.) in months.

The currentness of follow-up for survival, defined as the time between last OS contact (i.e., last known alive date or death date) and cutoff date (defined by last patient last visit date), will be summarized in months. Subjects who died and subjects with last known alive date on or after data cut-off date will have zero value for currentness of follow-up.

Minimum follow-up of OS, defined as the time from cutoff date to last subject's randomization date, will be summarized in months.

## **7.5.3 Interim/Final Analyses of Disease-Free Survival and Overall Survival**

In addition to the formal planned interim and final analyses of DFS and OS, the Data Monitoring Committee (DMC) will have access to periodic un-blinded interim reports of efficacy and safety to allow a risk/benefit assessment. Details are included in the DMC charter.

The DMC will review the safety and efficacy data from the informal interim analyses and will determine if the study should continue with or without changes or if accrual should be stopped. Subject enrollment will continue while waiting for the DMC's decisions.

The chair of the DMC and the sponsor can call an unscheduled review of the safety data.

At the time of the formal interim analysis for superiority of DFS, the DMC may recommend continuing or stopping the trial.

- If the trial continues beyond the formal interim analysis, the nominal critical point for the final DFS analysis will be determined using the recalculated information fraction at the time of the interim analysis, as described above. The final DFS hazard ratio and corresponding confidence interval will be reported whereby the confidence interval will be adjusted accordingly (i.e. using the recalculated nominal  $\alpha$  level at the final analysis).

- If the trial is stopped for superiority of DFS at the interim, the p-value from the interim stratified log-rank test will be considered the final primary analysis result.  
If allowed per hierarchical testing procedure, at the time of the formal interim analyses for superiority of OS, the DMC may recommend continuing or stopping the trial (see [Section 5.1](#)).
- If the trial continues beyond the two formal interim analysis, the nominal critical point for the final OS analysis will be determined using the recalculated information fraction at the time of each interim analyses, as described above. The final OS hazard ratio and corresponding confidence interval will be reported whereby the confidence interval will be adjusted accordingly (i.e. using the recalculated nominal  $\alpha$  level at the final analysis).
- If the trial is stopped for superiority of OS at one of the interim analyses, the p-value from the interim stratified log-rank test will be considered the final primary analysis result.

The same above procedure applies independently in each co-primary population.

#### **7.5.4 Non-Urothelial Tract Recurrence Free-Survival**

Similar analysis to primary endpoint of DFS will be conducted for NUTRFS, but no formal comparison between treatment groups will be done.

The NUTRFS function for each treatment group will be estimated using the KM product limit method and will be displayed graphically. A two-sided 95% CI for median NUTRFS in each treatment group will be computed via the log-log transformation method. NUTRFS rates at fixed time points (e.g. 6 months, depending on the minimum follow-up) will be presented along with their associated 95% CIs. These estimates will be derived from the Kaplan Meier estimate and corresponding CIs will be derived based on Greenwood formula for variance derivation and on log-log transformation applied on the survivor function.

The primary definition of NUTRFS adjusting for subsequent anticancer therapy will be used in this analysis. The two-sided log-rank p-value will be reported.

The source of NUTRFS event (recurrence or death) will be summarized by treatment group. The status of subjects who are censored (as per primary definition of NUTRFS) in the NUTRFS KM analysis will be tabulated for each treatment group including the following categories:

- On-study (on-treatment, in follow-up)
- Off-study (lost to follow-up, withdraw consent, never treated)
- No baseline disease assessment
- No on-study disease assessment and no death
- Received subsequent anticancer therapy
- New non-urothelial carcinoma primary cancer

#### **7.5.5 Disease-Specific Survival**

No formal comparison between treatment groups will be done.

## **7.6 Safety**

Analyses in this section will be tabulated for all treated subjects as well as for all treated subjects with PD-L1 expression  $\geq 1\%$  by treatment group as treated, unless otherwise specified.

### **7.6.1 Deaths**

Deaths will be summarized by treatment group:

- All deaths, reasons for death.
- Deaths within 30 days of last dose received, reasons for death.
- Deaths within 100 days of last dose received, reasons for death.

A by-subject listing of deaths will be provided for the all enrolled subjects population.

### **7.6.2 Serious Adverse Events**

Serious adverse events will be summarized by treatment group:

- Overall summary of SAEs by worst CTC grade (any grade, grade 3-4, grade 5) presented by SOC/PT.
- Overall summary of drug-related SAEs by worst CTC grade (any grade, grade 3-4, grade 5) presented by SOC/PT.

All analyses will be conducted using the 30-day safety window.

A by-subject SAE listing will be provided for the all enrolled subjects population.

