6.1.1 Serious Adverse Event Collection and Reporting

Sections 5.6.1 and 5.6.2 in the Investigator Brochure (IB) represent the Reference Safety Information to determine expectedness of serious adverse events for expedited reporting. Following the subject's written consent to participate in the study, all SAEs, whether related or not related to study drug, must be collected, including those thought to be associated with protocol-specified procedures. All SAEs must be collected that occur during the screening period and within 100 days of discontinuation of dosing.

Following the subject's written consent to participate in the study, all SAEs, whether related or not related to study drug, must be collected, including those thought to be associated with protocol-specified procedures. All SAEs must be collected that occur during the screening period and within 100 days of discontinuation of dosing. Subjects who are randomized and never treated with study drug, must have SAEs collected for 30 days from the date of randomization. If applicable, SAEs must be collected that relate to any later protocol-specified procedure (eg, a follow-up skin biopsy).

The investigator should report any SAE that occurs after these time periods and that is believed to be related to study drug or protocol-specified procedure.

An SAE report should be completed for any event where doubt exists regarding its seriousness.

If the investigator believes that an SAE is not related to study drug, but is potentially related to the conditions of the study (such as withdrawal of previous therapy or a complication of a study procedure), the relationship should be specified in the narrative section of the SAE Report Form.

SAEs, whether related or not related to study drug, and pregnancies must be reported to BMS (or designee) within 24 hours of becoming aware of the event. SAEs must be recorded on the SAE Report Form; pregnancies on a Pregnancy Surveillance Form (electronic or paper forms). The preferred method for SAE data reporting collection is through the eCRF. The paper SAE/pregnancy surveillance forms are only intended as a back-up option when the eCRF system is not functioning. In this case, the paper forms are to be transmitted via email or confirmed facsimile (fax) transmission to:

SAE Email Address: Refer to Contact Information list.

SAE Facsimile Number: Refer to Contact Information list.

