8.4.3 Safety Analyses

The safety analysis will be performed in treated subjects with PD-L1 expression level $\geq 1\%$ as well as in all treated subjects. Descriptive statistics of safety will be presented using NCI CTCAE version 4.0 by treatment arm. Adverse events, drug-related AEs, SAEs and drug-related SAEs will be tabulated using worst grade per NCI CTCAE v.4.0 criteria by system organ class and preferred term. On-study lab parameters including hematology, chemistry, liver function and renal function will be summarized using worst grade per NCI CTCAE v.4.0 criteria.

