APPENDIX 3 WOMEN OF CHILDBEARING POTENTIAL DEFINITIONS AND METHODS OF CONTRACEPTION

DEFINITIONS

Woman of Childbearing Potential (WOCBP)

A woman is considered fertile following menarche and until becoming post-menopausal unless permanently sterile. Permanent sterilization methods include hysterectomy, bilateral salpingectomy, and bilateral oophorectomy.

Women in the following categories are not considered WOCBP

- Premenarchal
- Premenopausal female with 1 of the following:
 - Documented hysterectomy
 - Documented bilateral salpingectomy
 - Documented bilateral oophorectomy

Note: Documentation can come from the site personnel's review of the participant's medical records, medical examination, or medical history interview.

- Postmenopausal female
 - A postmenopausal state is defined as 12 months of amenorrhea in a woman over age 45 years in the absence of other biological or physiological causes. In addition, females under the age of 55 years must have a serum follicle stimulating hormone, (FSH) level > 40 mIU/mL to confirm menopause.

Note: Females treated with hormone replacement therapy, (HRT) are likely to have artificially suppressed FSH levels and may require a washout period in order to obtain a physiologic FSH level. The duration of the washout period is a function of the type of HRT used. The duration of the washout period below are suggested guidelines and the investigators should use their judgement in checking serum FSH levels.

- 1 week minimum for vaginal hormonal products (rings, creams, gels)
- 4 week minimum for transdermal products
- 8 week minimum for oral products

Other parenteral products may require washout periods as long as 6 months. If the serum FSH level is > 40 mIU/ml at any time during the washout period, the woman can be considered postmenopausal.

CONTRACEPTION GUIDANCE FOR FEMALE PARTICIPANTS OF CHILD BEARING POTENTIAL

One of the highly effective methods of contraception listed below is required during study duration and until the end of relevant systemic exposure, defined as 5 months after the end of study treatment.

Local laws and regulations may require use of alternative and/or additional contraception methods.

Highly Effective Contraceptive Methods That Are User Dependent
 
Failure rate of <1% per year when used consistently and correctly.^a

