## 6 STUDY PERIODS, TREATMENT REGIMENS AND POPULATIONS FOR ANALYSES

### 6.1 Study Periods

- Baseline period:
  - Baseline evaluations or events will be defined as evaluations or events that occur before the date and time of the first dose of study treatment. Evaluations (laboratory tests and vital signs) on the same date and time of the first dose of study treatment will be considered as baseline evaluations. Adverse Events (AEs) on the same date and time of the first dose of study treatment will not be considered as pre-treatment events.
  - In cases where the time (onset time of event or evaluation time and dosing time) is missing or not collected, the following definitions will apply:
    - ◆ Pre-treatment AEs will be defined as AEs with an onset date prior to but not including the day of the first dose of study treatment;
    - ◆ Baseline evaluations (laboratory tests and vital signs) will be defined as evaluations with a date on or prior to the day of first dose of study treatment.
  - If there are multiple valid assessments on or prior to the first dose of study treatment:
    - [REDACTED]
    - [REDACTED]
    - ◆ For PD-L1, among the biopsy samples records taken prior to or on first dose date (and time if collected), identify first those with quantifiable test result. If there are no records with quantifiable test result, then select those with indeterminant result (“INDETERMINATE”). If there are no records with indeterminant test result, then select those with unavailable result (“NOT EVALUABLE”). If there are no records with unavailable test result, then select those with not reported or not available result (all other records). The latest record will be used as the baseline in the analyses. If there is more than one record for the latest date, then choose the one with the greatest specimen ID.
    - [REDACTED]

- Post baseline period:
  - On-treatment AEs will be defined as AEs with an onset date and time on or after the date and time of the first dose of study treatment (or with an onset date on or after the day of first dose of study treatment if time is not collected or is missing). For subjects who are off study treatment, AEs will be included if event occurred within a safety window of 30 days (or 100 days depending on the analysis) after the last dose of study treatment. No “subtracting rule” will be applied when an AE occurs both pre-treatment and post-treatment with the same preferred term and grade.

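### The two SAE summary tables in SAP 7.6.2 stop at 30 days after last dose, although SAEs are collected to 100 days and the SAP already has a 100-day window

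*SAP*

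**What the plan says.** **Collection.** Protocol 6.1.1 covers SAEs whether or not related to study drug: "All SAEs must be collected that occur during the screening period and within 100 days of discontinuation of dosing". Protocol 6.2.1 sets the same minimum of 100 days for nonserious events.

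**Protocol analysis.** Protocol 8.4.3 states: "Adverse events, drug-related AEs, SAEs and drug-related SAEs will be tabulated using worst grade per NCI CTCAE v.4.0 criteria". It gives no time window.

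**SAP windows.** SAP 6.1 defines on-treatment adverse events with a post-dose window of either 30 or 100 days and leaves the choice to each analysis. It defines late-emergent drug-related events as those starting more than 100 days after the last dose.

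**SAE outputs.** SAP 7.6.2 lists a summary of all SAEs by treatment group and a second one, described as "Overall summary of drug-related SAEs by worst CTC grade (any grade, grade 3-4, grade 5) presented by SOC/PT". Of these it says: "All analyses will be conducted using the 30-day safety window". The only other output in the section is a listing: "A by-subject SAE listing will be provided for the all enrolled subjects population".

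**Deaths.** SAP 7.6.1 tabulates deaths by treatment group at any time, within 30 days and within 100 days of last dose, with reasons.

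**The concern.** The protocol asks sites to ascertain SAEs for 100 days and to see subjects in person during safety follow-up (Protocol 5.3). It also defines immune-mediated events over 100 days from last dose (Protocol 6.2.2). The SAP has the matching window ready and applies it to deaths. SAEs, the next most serious category, get only the shorter window, and the visible text gives no reason.

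Subjects enter this trial free of disease after surgery, and the sample size model treats 32% of controls as cured. Serious toxicity that appears after treatment stops bears directly on benefit and risk in such a population. A reader who relies on the two SAE tables for the comparison between arms would not see non-fatal SAEs that began on days 31 to 100. Those events would have to be counted by hand from a listing.

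**Working it through.** The documents state no figure on this point, so there is nothing to reproduce. The check compares the collection and analysis windows and then sizes the difference.

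**Step 1. Which output covers which post-dose days**

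| Output | Source | Post-dose days covered | Compared by arm? |
|---|---|---|---|
| SAE collection | Protocol 6.1.1 | 0 to 100 | not applicable |
| All SAEs, drug-related SAEs | SAP 7.6.2 | 0 to 30 | yes |
| SAE listing | SAP 7.6.2 | no limit stated | no |
| Deaths | SAP 7.6.1 | 0 to 30, 0 to 100, any time | yes |
| Late-emergent drug-related events | SAP 6.1 | after 100 | not stated in the visible text |

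I read the listing as unrestricted. It covers all enrolled subjects, including those never treated, for whom a window after last dose has no meaning.

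The late-emergent category begins where the 100-day window ends, so it does not pick up days 31 to 100. The 100-day death table picks up fatal outcomes. What remains is non-fatal SAEs with onset on days 31 to 100.

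**Step 2. Share of post-dose collection time**

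100 − 30 = 70 days, and 70 / 100 = 70%.

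This is a share of calendar days after the last dose. It is not a share of SAEs.

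**Step 3. Share of total at-risk time**

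Let D be the duration of study therapy in days. With the 100-day window a fully followed subject contributes D + 100 days, which matches the SAP's person-year rule (last dose − first dose + 101 days). The excluded share is 70 / (D + 100).

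| D (days) | D + 100 | 70 / (D + 100) |
|---|---|---|
| 365 (maximum treatment, 1 year) | 465 | 15.1% |
| 180 (assumed) | 280 | 25.0% |
| 90 (assumed) | 190 | 36.8% |
| 1 (single dose, assumed) | 101 | 69.3% |

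The share is larger for subjects who stop early, including those who stop for toxicity.

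**Step 4. Number of events**

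Neither document gives SAE rates by arm or by time since last dose. The count of SAEs on days 31 to 100 and its split between arms cannot be computed.

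**The case against.** The strongest reply is that a collection period is not an analysis window. Protocol 8.4.3 names no window, SAP 6.1 leaves the choice to each analysis, and SAP 7.6.2 makes it. The same 30-day choice appears in SAP 7.6.3, 7.6.4 and 7.6.16. This stands: a reader might infer that the SAP breaches the protocol, and it does not.

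Second, the SAP contents list sections on adverse events, select adverse events, immune-mediated adverse events, other events of special interest and multiple events (within 7.6.5 to 7.6.14), and their text is not visible. The SAP's general methods allow rates per 100 person-years with a 100-day option. Serious late immune-related events may therefore enter a comparative table there. This also stands: the documents do not support saying that late immune toxicity has no between-arm summary. It does not close the gap, because 7.6.2 fixes the window for its own SAE tables. Under the protocol's definition, an immune-mediated table would be limited to listed categories and, apart from endocrine events, to subjects given immunosuppression.

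Third, a reader might infer that the under-count falls mainly on nivolumab. The window is the same in both arms and no rates are given, so the direction is not shown. The contraception period of 5 months in Protocol Appendix 3 does not help either, because it is not a window for attributing toxicity.

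Fourth, a longer window has a cost for interpretation. Subjects stop study drug at recurrence and may then receive other anticancer therapy, so some all-cause SAEs on days 31 to 100 will reflect disease or later treatment. If recurrence differs by arm, so will those events. A footnote alone would not deal with this, and the fix has to.

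**Conclusion.** The point holds as a worthwhile, low-cost addition to the safety analysis. Both SAE summaries in SAP 7.6.2 leave out non-fatal SAEs with onset on days 31 to 100, although those events must be collected and the SAP already has a window that would include them.

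The size is 70 of 100 post-dose collection days, or about 15% of at-risk time after a full year of treatment and more for shorter treatment. The 70% should not be read as a proportion of SAEs missed, since SAEs during treatment and up to day 30 are all counted. The shares of at-risk time assume that each subject is followed for the whole 100 days, and durations under one year are illustrations.

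The conclusion rests on the wording of 7.6.2 alone. It is confined to the SAE tables in that section and makes no claim about the sections that cannot be seen. No efficacy conclusion, alpha level or sample size is affected, and the late events remain in the listing.

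**What to change.** Keep the 30-day tables. Add to SAP 7.6.2 that both summaries (all SAEs, and drug-related SAEs, by worst grade and by system organ class and preferred term) will be repeated with the 100-day window for the two populations named in SAP 7.6: all treated subjects and treated subjects with PD-L1 expression of at least 1%.

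In the 100-day tables, flag SAEs with onset after the start of subsequent anticancer therapy, or present them separately. Subsequent therapy is already collected in follow-up (Protocol Table 5.1-3) and summarized under SAP 7.4.3.2.

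If the sponsor prefers 30 days only, the SAP should say why. If a section not visible here already gives SAEs by arm over 100 days, a cross-reference from 7.6.2 is enough.

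Cost: two summaries in two populations, so four more tables, from data already collected and a window already defined. The downside is that some all-cause events in the longer window will reflect recurrence or later therapy. Separate presentation makes those after later therapy visible but does not remove the confounding.
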